10.3 Interim analyses and stopping rules

No interim analyses were conducted for primary or secondary outcomes. The Data Safety and Monitoring board is granted the power to recommend discontinuation of the study to the IRB, if safety concerns are found. The DSMB will meet at least three times over the course of the study: prior to the commencement of the study, at approximately month 9 of the intervention period, and at the end of the intervention period. Additional meetings will occur as needed or as directed by the study sponsor. Following each meeting, the board will make recommendations to the IRB as to whether the study should continue or if changes to the protocol are needed.

10.4 Outcomes

10.4.1 Co-primary outcomes

This study has 3 co-primary outcomes, referred to as PSA, UA/UC, and DM (defined in Section 6 above). They capture the over-testing, over-screening, and over-treatment of older patients, who may need less care than they are receiving. The ICD-10 codes used to capture these co-primary outcomes are defined in detail in the Supplement to this document. These outcomes are computable clinical quality measures that are abstracted from the EHR. They were previously validated as part of pilot work for this study. These will be extracted from the EHR on a monthly basis, with data for each month representing a 365 look-back period.

An office visit will be eligible for inclusion in the outcome denominator if it meets the following criteria:

PSA. Men were eligible for the PSA over-screening measure if they were age 76 years or older and attended at least one visit in the 365 days prior to the measurement date (for example, 365 days prior to February 1, 2020) with a clinician included in the study. Eligible patients had no history of prostate cancer (determined via diagnosis or procedure code) and were not taking an androgenic agent or anabolic steroid as of the measurement date.

UA/UC. Women were eligible for the urine testing for non-specific reasons (UA/UC) measure if they were age 65 years or older and had an in-person ambulatory care visit with a participating clinician in the 365 days prior to the measurement date where a urinalysis and/or urine culture was obtained in the interval 24 hours before to 48 hours after the visit. If a woman had multiple qualifying visits in the 365-day window, only the first was included.

DM. Patients were eligible for the diabetes over-treatment measure if they were age 75 years or older with a diagnosis of diabetes mellitus and their most recent hemoglobin A1C in the 365 days prior to the measurement date was less than 7.0%. Patients were attributed to the primary care clinician with whom they had the greatest number of visits in the 365-day window.

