4.2 Patient eligibility

All patients aged 65 years and older will be included in the overall study patient population. We will assess study outcomes for all clinics, clinicians and individual patients who meet the pre-defined study eligibility criteria for each measure.

Co-Primary Outcome	Eligibility Criteria
PSA	All adult men aged 76 years and older with a visit to a participating primary care or geriatrics NM clinic between September 1, 2018 – February 28, 2023
DM	All adults aged \geq 75 years old with a visit to a participating primary care or geriatrics NM clinic visit between September 1, 2018 – February 28, 2023
UA/UC	All adult women aged 65 years and older with at least one primary care, geriatrics, or immediate care NM visit between September 1, 2018 – February 28, 2023

Note: all subjects over the age of 89 years will be aggregated into a single category. We will obtain these outcomes by queries of the NMEDW. Some data are prospective in that they do not exist at the time of

IRB submission but retrospective in that we will only have access to them after collected in NM Epic as part of routine care delivery.

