5. STUDY INTERVENTIONS

5.1 Definitions of Study Interventions

Clinician education (control). An interactive educational module (15-20 minutes) covering the three targeted areas of overuse.

Clinical decision support plus clinician education (intervention).

Best Practice Advisories were programmed into Epic to present content to the clinician and feature functionality to add content to the encounter documentation. Clinicians attributed to clinics in the ‘CDS intervention + Education’ arm receive CDS alerts when conditions within a chart meet triggering criteria. For example, a CDS alert appears when a clinician places an order for a PSA test when the patient meets qualifying criteria (e.g., ≥ 76 years old, no prior prostate cancer). The CDS alerts encourage the clinician to cancel the order in the cases of PSA and urine testing or to decrease diabetes medication in the case of diabetes overtreatment (Table 1); however, they do not restrict clinical decision making in any way. If the clinician proceeds with the order for the PSA, urinalysis, or urine culture they are asked to enter text justifying the order. This justification is then included within the encounter report, visible to any clinician within the chart, under a heading titled ‘Testing Justification’. If the clinician does not enter a justification, the note “No justification given” is included in the encounter report.[9, 10] Images of the CDS presented to the clinicians for each alert and triggering criteria are included in the supplemental material. The EHR programming logic used in the pilot study was re-tested for this trial.

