6. STUDY ENDPOINTS

6.1 Primary endpoints

Our team developed and validated by manual chart review three electronic clinical quality measures (one associated with each of the 3 study interventions). These measures will be abstracted from the EHR once a month for the duration of the intervention period. The three co-primary endpoints are:

PSA. The PSA screening in older men (PSA) measure is defined as the presence of a PSA laboratory result in the EHR during the measurement period among men aged 76 years and older at the start of the measurement period with at least one visit during the measurement period with a clinician included in the study and who are without a diagnosis or procedure suggesting a history of prostate cancer (Protocol Supplement 2, pg. 4). Patients on androgenic agents or anabolic steroids are excluded (Protocol Supplement 2, pg. 7). Labs constituting the numerator are provided in Protocol Supplement 2 (pg. 7). Patients are attributed to the primary care clinician with whom they have the greatest number of visits during the measurement period. The measurement period consists of the 365 days preceding the measurement date.

UA/UC. Urine Testing for Non-Specific Reasons (UA/UC) is defined as the absence of a diagnostic code for a specific genitourinary sign, symptoms or other potentially relevant indication (Protocol Supplement 3, pg. 8) among instances where a urinalysis (UA) and/or urine culture (UC) is obtained in the interval 24 hours before to 48 hours after a face-to-face ambulatory care visit by a woman aged 65 years or older with a qualifying clinician during the study period. Testing episodes are attributed to the clinician who ordered the test. Only UA and/or UC ordered by a qualifying clinician are included. Only the first testing episode in a measurement period is included in patients with multiple qualifying visits. The measurement period is the 365 days preceding the measurement date.

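### The UA/UC co-primary is a share among tested women, and the alert acts on the decision to test, so a fall in that share does not by itself show fewer non-specific tests

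*Combined protocol and SAP*

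**What the plan says.** The précis and section 1.1 set the aim as less ordering of urine tests for non-specific reasons in women aged 65 and over. The précis describes each co-primary as recording whether an eligible patient received care that was not needed.

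The outcome definition is narrower. Section 6.1 says that the measure "is defined as the absence of a diagnostic code for a specific genitourinary sign, symptoms or other potentially relevant indication", and takes it "among instances where a urinalysis (UA) and/or urine culture (UC) is obtained" around an ambulatory visit. Section 10.4.1 applies the same restriction, requiring an in-person "visit with a participating clinician in the 365 days prior to the measurement date where a urinalysis and/or urine culture was obtained". Section 6.1 adds: "Only the first testing episode in a measurement period is included in patients with multiple qualifying visits".

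Section 4.2 describes the UA/UC population as "All adult women aged 65 years and older with at least one primary care, geriatrics, or immediate care NM visit", with no requirement of a test. The PSA measure in section 10.4.1 counts men with a visit, tested or not.

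On the intervention, section 5.1 states: "The CDS alerts encourage the clinician to cancel the order in the cases of PSA and urine testing". Clinicians who go ahead with the order are treated differently: "they are asked to enter text justifying the order".

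The co-primaries are analysed by mixed-effects logistic regression (section 10.5) and reported as marginal monthly rates (précis). Table 1 gives power as absolute reductions and relative risks. Total urinalysis and total urine culture use are secondary outcomes (section 10.4.2). The main text plans no analysis of change in the number of women tested or in coding.

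**The concern.** Randomization makes the arms comparable for all women who visit. It does not do so for women who are tested, because in one arm the alert influences who is tested. A cancelled non-specific test usually takes the woman out of both numerator and denominator, so she is not counted as a woman who avoided a test.

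The numerator is the lack of a code, and only the intervention arm is prompted to document a reason. The measure could therefore respond to documentation as well as to testing.

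At stake is how one of three co-primary results can be read. A lower share need not mean fewer non-specific tests, and an unchanged share need not mean that none were avoided. PSA has the same kind of cancel-the-order alert but does not have the denominator problem.

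**Working it through.** **Inputs.** Baseline shares p of 20%, 25% and 30%, with minimum detectable reductions of 3.8, 4.2 and 4.4 points, N = 15,000, 60 clinics, intraclass correlation (ICC) 0.017, two-sided alpha 0.05/3 and 80% power (section 10.2 and Table 1). The 20% response used below is an assumption.

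**1. Table 1.** The relative risks reproduce: 16.2/20 = 0.81, 20.8/25 = 0.83, 25.6/30 = 0.85. The reductions do not. With 15,000/60 = 250 women per clinic, the design effect is 1 + 249 × 0.017 = 5.233 and the effective number per arm is 7,500/5.233 = 1,433. Solving a two-proportion test for 80% power gives 4.6, 5.0 and 5.4 points. An ICC near 0.010 would match the printed values. That is a separate matter. Table 1 serves here only as the plan's own yardstick.

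**2. Cancelling a fraction c of non-specific tests**, with indicated tests unchanged and no later test: new share = p(1−c)/(1−pc). **Adding a code to the same fraction**, with no test avoided: new share = p(1−c). With c = 0.20:

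| p | Share after cancelling | Drop (points) | Relative risk | Table 1 limit | Drop after recoding |
|---|---|---|---|---|---|
| 20% | 0.16/0.96 = 16.7% | 3.3 | 0.83 | 3.8 | 4.0 |
| 25% | 0.20/0.95 = 21.1% | 3.9 | 0.84 | 4.2 | 5.0 |
| 30% | 0.24/0.94 = 25.5% | 4.5 | 0.85 | 4.4 | 6.0 |

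Non-specific tests fall by 20% in every cancelling case, yet the relative risk shows 15% to 17%. The drop is below Table 1's limit at 20% and 25%, and just above it at 30%.

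**3. Odds scale.** After cancelling, the odds are p(1−c)/(1−p), so the odds ratio is 1−c = 0.80 at every baseline. There is no attenuation on this scale if indicated tests are unchanged.

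**4. Indicated tests also deterred, by a fraction d.** New share = p(1−c)/[p(1−c) + (1−p)(1−d)]. With p = 25%:

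- c = d = 0.20: 0.20/(0.20 + 0.60) = 25.0%. There is no effect on any scale.
- c = 0.10, d = 0.20: 0.225/(0.225 + 0.60) = 27.3%. The share rises although non-specific tests fell.

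**5. Response needed to reach Table 1's reductions** (p = 20%, 25%, 30%). By cancelling, 22.7%, 21.2% and 19.7% of non-specific tests. By recoding with no test avoided, 19.0%, 16.8% and 14.7%.

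**6. Later tests.** A woman whose order is cancelled and who later has an indicated test in the window stays in the denominator as a non-event. If all did, the 25% share would fall to 20.0% rather than 21.1%.

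**7. Power of a per-woman rate.** The documents do not give the fraction t of visiting women who are tested. Assume t = 20% to 50%, 15,000 tested women, p = 25%, 21.2% of non-specific tests avoided and an ICC still 0.017.

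- t = 20%: N = 75,000, rate 5.0% to 3.9%, design effect 1 + 1,249 × 0.017 = 22.2, power about 18%.
- t = 50%: N = 30,000, rate 12.5% to 9.9%, design effect 1 + 499 × 0.017 = 9.5, power about 49%.

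The share itself has about 61% under the same inputs.

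**The case against.** The strongest reply is that the planned test is on the log-odds scale, where step 3 shows no attenuation. A reader might infer that the measure understates avoided tests on every scale. The plan does not support that unless indicated tests are deterred too. Whether they are depends on the alert's trigger criteria, which are in supplements not shown; an alert that fires only when no indication is recorded would largely spare them. The reply stands for the odds ratio. It does not cover the marginal rates to be reported or the absolute reductions and relative risks in Table 1.

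A reader might also infer that the alert changes coding. Section 5.1 describes free text and mentions no diagnosis code, so recoding is a possibility and not a documented effect. The total UA and total UC outcomes would partly expose it, but they are secondary, are not split by indication, and are not tied to the co-primary conclusion.

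The comparison with Table 1 depends on the assumed response. The pilot in section 2.2 reports no test ordered after 21 of 34 alerts (62%), with no comparison group described. If 62% of non-specific tests were cancelled at a 25% baseline, the share would be 0.095/0.845 = 11.2%, a drop of 13.8 points. A shortfall against Table 1 is therefore not a general result.

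Finally, section 4.2 can be read as a source frame. Its DM row omits the diabetes diagnosis and its PSA row omits the prostate cancer exclusion, and sections 6.1 and 10.4.1 supply the details. That is fair. The relation between the sections needs stating, but it need not be a contradiction.

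**Conclusion.** The concern holds as a limit on interpretation and should be fixed. The UA/UC co-primary conditions on being tested, which the intervention is designed to change, so the share alone cannot establish that fewer non-specific tests were done.

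The size depends on assumptions. At an assumed 20% response with no later testing, the absolute and relative effects on the share are modestly attenuated and the odds ratio is not. If indicated tests are deterred equally, the effect vanishes on all scales. If clinicians recode, an effect appears without any test avoided. The documents do not show which of these would occur.

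A reader might conclude that the co-primary must be replaced. The documents do not support going that far. The share was validated by chart review (section 6.1), and its clinic-level rate was one of the constrained-randomization variables (section 10.2). A per-woman rate could lose considerable power, and its event would still depend on a code, so it would not by itself guard against recoding.

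**What to change.** 1. In sections 10.4.1 and 10.5, add a pre-specified key analysis of non-specific UA/UC per woman aged 65 or over with a qualifying in-person visit to a participating clinician, tested or not.
2. State that a conclusion of reduced non-specific testing requires this result, and the between-arm results for total UA and total UC per eligible woman, to point the same way. The totals are needed because the per-woman event alone does not protect against recoding.
3. Report by arm the number of women tested and the share of tests with an indication code.
4. Keep the validated share as the co-primary and describe it as appropriateness among tested women.
5. State whether N = 15,000 in Table 1 means tested or visiting women. Clarify how the section 4.2 population, including immediate-care visits, relates to section 10.4.1.
6. If outcome data have already been seen, label and date the addition.

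The cost is revised wording, one more denominator query in the data warehouse, and some extra analysis. The per-woman rate will be lower than Table 1's 20% to 30% and may have less power than Table 1 shows, so its expected precision should be stated once the tested fraction is known.

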5.3 Interruption due to COVID-19 Pandemic

The intervention period for BEAGLE was originally slated to begin in April 2020. However, on March 21, 2020, the governor of Illinois and mayor of Chicago issued a “stay-at-home” order to mitigate harm from the COVID-19 pandemic. This severely impacted regular primary care activities at Northwestern Medicine. As such, we chose to delay the start of the intervention until regular care resumed. The intervention was rolled out on September 1, 2020, and the look-back period for the study measures was adjusted to exclude data collected between March 1, 2020 and August 31, 2020. So, for example, study outcomes reported in December 2020 included the following 12 months of data: June 1, 2019 – February 29, 2020 plus September 1, 2020 – November 30, 2020.

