DM. Diabetes Overtreatment in the Elderly (DM) is defined as the having the most recent hemoglobin A1C during the measurement period or during the year prior to the measurement period (if no A1C obtained during the measurement period) of less than 7.0 among adults aged 75 years and older with a diagnosis of diabetes mellitus who have insulin or an oral hypoglycemic (e.g., sulfonylurea or meglitinide, Protocol Supplement 4, pg. 12) on their active medication list at the end of the study period. Patients are attributed to the primary care clinician with whom they had the greatest number of visits during the measurement period. The measurement period is the 365 days preceding the measurement date.

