10. STATISTICAL CONSIDERATIONS

10.1 General Design Overview

Hypotheses

Our primary hypothesis is that practices randomized to receive behavioral economic interventions will have decreases over time in the over-screening, over-treatment, and over-testing of older patients who

may no longer warrant such care. This hypothesis will be evaluated in an intention-to-treat difference-in-differences framework using a mixed-effects logistic regression model. Fixed effects will include the effects of interventions over time (i.e., interactions between randomization assignment and time), using a historical period 12 months prior to the intervention period. Providers and randomization unit (clinic) will be modeled as random effects.

Design

We will conduct a cluster randomized trial using data abstracted from the EHR at one academic health system. We chose a cluster-randomized design at the clinic level to minimize spillover effects – contamination that might occur if individual providers in close proximity are randomized to different interventions. The study design for BEAGLE included the implementation of a modified constrained randomization scheme, to ensure that clinics in each study arm were similar prior to activation of the intervention.

Outcome measures

This study has 3 co-primary outcomes, referred to as PSA, UA/UC, and DM (defined in Section 6 above, and further detailed in Section 10.4 below). They capture the over-testing, over-screening, and over-treatment of older patients, whose medical needs may have evolved to require less care.

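### The DM co-primary is defined inconsistently: A1C below 7.0 is the event in Section 6.1 but a condition for entering the denominator in Section 10.4.1, and Table 1 and randomization variables 7 and 8 do not say which version they use.

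*Combined protocol and SAP*

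**What the plan says.** All references are to the combined protocol and SAP.

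- **Section 6.1 (DM).** The event is a most recent A1C below 7.0. The A1C may come from the measurement period "or during the year prior to the measurement period (if no A1C obtained during the measurement period) of less than 7.0". The denominator is adults aged 75 and over with diabetes who have insulin or a listed oral hypoglycemic "on their active medication list at the end of the study period". On frequency, the same section says: "These measures will be abstracted from the EHR once a month for the duration of the intervention period".
- **Section 10.4.1.** The criteria are introduced with "An office visit will be eligible for inclusion in the outcome denominator if it meets the following criteria". For DM they are age 75 or over, a diabetes diagnosis, and that "their most recent hemoglobin A1C in the 365 days prior to the measurement date was less than 7.0" percent. There is no drug condition and no prior-year fallback.
- **Section 10.1.** The co-primary outcomes are "defined in Section 6 above, and further detailed in Section 10.4 below". Section 10.4.1 also refers back to Section 6 for the definitions.
- **Section 10.2.** Table 1 plans DM on N = 6,600 with baseline rates of 15, 20 and 25%. Randomization variables 7 and 8 are the count of DM-eligible patients and the annual DM overtreatment rate. Neither place gives the DM criteria.
- **Section 5.3.** Because of the pandemic, "the look-back period for the study measures was adjusted to exclude data collected between March 1, 2020 and August 31, 2020".

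**The concern.** The same laboratory result is the outcome in one section and the ticket of entry in the other. For PSA and UA/UC, the denominators in 10.4.1 match 6.1 in substance. Only for DM does the condition that 6.1 treats as the event move into the denominator while the drug condition disappears, so this is not just a shorter restatement.

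Three things are at stake. First, one of three co-primary outcomes has no single estimand: a treated patient with A1C of 7.0 or above is a non-event under 6.1 and is absent under 10.4.1. Second, the planned power and the balance on variables 7 and 8 cannot be tied to the outcome that will be analysed. Section 10.5 also puts the randomization variables into the model as covariates, and the hypoglycemia secondary outcome in 6.2 is counted among eligible patients, so both inherit the ambiguity. Third, 6.1 taken literally selects patients in every month, baseline included, on a drug status observed after randomization.

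**Working it through.** **1. The plan's own figure.** Inputs from Section 10.2: N = 6,600, 60 clinics (110 patients each), ICC 0.017, two-sided alpha 0.05/3, power 80%. The design effect is 1 + (110 − 1) × 0.017 = 2.853, so effective n per arm is 3,300/2.853 = 1,157. I solved d√n = z(1−α/2)·√(2p̄(1−p̄)) + z(0.80)·√(p₁(1−p₁) + p₂(1−p₂)), with p₂ = p₁ − d and p̄ their mean.

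| Setting | 15% | 20% | 25% |
|---|---|---|---|
| Table 1 | 3.9 | 4.4 | 4.8 |
| ICC 0.017, alpha 0.05/3 (as stated) | 4.49 | 5.10 | 5.59 |
| ICC 0.017, alpha 0.05 | 3.92 | 4.45 | 4.87 |
| ICC 0.010, alpha 0.05/3 | 3.88 | 4.40 | 4.81 |

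The row is not reproduced with the stated inputs by this approximation. It is reproduced, to within 0.1 point, by either of two changes. That is a separate matter. What counts here is that N and the baseline rate enter as bare numbers, so no version of this calculation shows which DM definition they came from.

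**2. The two definitions side by side.**

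| | Section 6.1 | Section 10.4.1 |
|---|---|---|
| A1C below 7.0 | event | denominator criterion |
| Listed drug active | denominator criterion | not mentioned |
| Prior-year A1C if none in the period | allowed | not mentioned |
| Time of drug status | end of study period | not applicable |

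**3. Joining them.** With 6.1's event and 10.4.1's denominator, everyone in the denominator has the event: rate = P(A1C < 7.0 given A1C < 7.0) = 100%. The sections therefore cannot be combined into one measure as printed.

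**4. Overlap, if Table 1 came from 6.1.** Patients in 6.1's denominator who also meet 10.4.1's entry condition are 6.1's events, less those who qualify only through the fallback year. Hence overlap ≤ 6,600 × rate:

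- 15%: at most 990; at least 5,610 outside
- 20%: at most 1,320; at least 5,280 outside
- 25%: at most 1,650; at least 4,950 outside

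This needs no assumption about the event in 10.4.1. The 10.4.1 denominator would also add patients with A1C below 7.0 and no listed drug; the documents give no count for them, so the rate under the other section cannot be computed.

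**5. Drug status at the end of the study.** Take a patient treated at baseline whose listed drugs are stopped during the intervention. Under 6.1 read literally, this patient is outside the denominator in every month, including the 12 baseline months. The stop cannot then appear as a change from baseline to intervention, although Section 5.1 says the DM alert encourages decreasing medication.

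**6. Fallback under 5.3.** The worked example for December 2020 uses 1 June 2019 to 29 February 2020 plus 1 September to 30 November 2020. The oldest usable A1C under 10.4.1 is then about 18 months old. Under 6.1, assuming that the prior year means the 12 months before 1 June 2019, it is about 30 months old. The documents do not say where the fallback year falls.

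**The case against.** The strongest reply is that Section 6 governs. Both 10.1 and 10.4.1 say the outcomes are defined there, and 10.4 only adds detail. A single study analyst extracts the data (11.2), and the measures are described as computable and validated, so one working definition probably exists. Section 10.4.1 lists denominator criteria only, for all three outcomes, so the lack of a stated DM numerator there is not a fault in itself. The end-of-study wording may be loose, since the UA/UC text in 6.1 also says study period where a 365-day measurement period applies.

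Much of this stands. A reader might infer that neither section takes precedence; the cross-references do favour 6.1. They do not settle the matter, because the added detail contradicts what it is meant to detail, and the documents do not say which text the validated code follows. The drug list supplement and the protocol paper were not available to me. They might show what was coded, but the conflict is in the body text.

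Other stronger readings are tempting and do not hold:

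- Section 4.2 might look like a third definition, since its DM row asks only for age and a visit in a date range. It is a visit frame for all three measures: its PSA row omits the prostate cancer exclusion and its UA/UC row omits the test.
- Section 5.3 might seem silent on how the 365 days move. Its worked example shows it; only the fallback year is left open.
- One might infer that the version balanced at randomization must be the co-primary. Nothing in the documents requires that. The PSA rate was itself not balanced, and the model adjusts for the randomization variables.

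**Conclusion.** Wrong as written. Two current sections give different populations for one co-primary outcome, and 6.1's timing of drug status does not fit a monthly measure. The contradiction rests on the text alone.

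The size is conditional. If N = 6,600 and the assumed 15 to 25% came from 6.1, at most 990 to 1,650 of those patients would be eligible under 10.4.1, and at least 75 to 85% would not. That treats Table 1's planning rates as the 6.1 rates; the realised rates are not given.

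A reader might go further and infer that the DM analysis was run on the wrong patients, that a 100% rate would be reported, or that the DM power is wrong for this reason. The documents support none of these. They show only that power and balance for DM cannot be traced to a stated outcome.

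**What to change.** 1. State which DM definition was validated and coded, and which produced Table 1's DM row and randomization variables 7 and 8.
2. Print that one definition in both 6.1 and 10.4.1, with the same numerator, denominator and A1C look-back. Say whether the prior-year fallback applies and, if so, which 12 months it covers under 5.3's exclusion.
3. Where 6.1 takes drug status "on their active medication list at the end of the study period", take it at the measurement date.
4. Restate Table 1's DM row if its baseline rate or N changes.
5. If outcomes have already been examined by arm, label any change post hoc and report both versions.

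Cost: text edits only, if the code already uses one version throughout with monthly drug status. Otherwise one re-query of the data warehouse and a revised Table 1 row.
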